
STUDY AIMS

Based upon previous research by [name] (PI) and her study team ([HUM00157016](#)), this study will pilot a physician-directed communication focused intervention, WE CHATT. The development of WE CHATT was informed by patients and their caregivers, with the ultimate goal of improving patient-centered communication for young people with advanced heart disease. The primary outcome of this pilot study is determining feasibility and acceptability, however, in the future, WE CHATT aims to (1) improve patient-centered communication with young people with advanced heart disease and (2) increase physician comfort in communicating with young people themselves regarding their communication needs and preferences.

METHODS

Recruitment and Sample

Physicians. A total of 20 physicians will be recruited. 10 will be randomized to participate in the intervention arm and 10 will be randomized to the control arm. Physician participants will be recruited from the Division of Pediatric Cardiology at the University of Michigan, which is currently comprised of 37 attending physicians and 16 fellows. All physicians with dedicated clinical effort will be eligible. Eligible physicians must anticipate remaining on staff ≥ 1 years. Study PI ([name]) and Co-I ([name]) will co-lead recruitment efforts via presentation(s) of study objectives and procedures at faculty/fellow meetings. Cardiology faculty and fellows were informally surveyed regarding interest in participating in the study. Over 90% of faculty and fellows expressed openness to participating in the study. Thus, the recruitment goal of 20 physician participants is feasible.

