Patient/Caregivers. Patients (12-24 years) with heart failure symptoms meeting criteria for New York Heart Association (NYHA) Class II - IV heart failure will be eligible (i.e., limitations in physical activity, fatigue, palpitations, dyspnea). One parent/caregiver of patient participants meeting inclusion criteria will also be eligible. This patient age range was selected in accordance with research in other illness groups,^{48,49,51} is consistent with the World Health Organization's definition of adolescent/young adult (AYA), and fulfills the Institute of Medicine's need for research on AYA end of life care preferences and decision making involvement.²⁹ This age range also captures the average age (17 years) of patients with congenital heart disease.³⁸ A *new patient* meeting the above criteria in any hospital setting (inpatient, outpatient cardiology clinic, emergency room) being cared for by a participating physician will be eligible for the study. Patients with significant cognitive/developmental delay with potential to impact study participation will be excluded from the study due to the focus on physician-youth communication. Parents and parent/caregivers who are non-English speaking will be excluded from this pilot study.

Compensation for Time. Intervention arm physician participants will receive a \$100 gift card for their time to complete surveys, attend intervention training, and engage in intervention with patient participants. Control arm physician participants will receive a \$25 gift card for their time completing surveys. All patient and parent/caregiver participants will receive a \$25 gift card for their time completing surveys.

Procedures

Intervention Arm. The WE CHATT communication-tool was developed based upon mixed-methods research and stakeholder engagement (patients, parents, physicians, nurses, hospital leadership) led by study PI, [name], over the past decade. It involves the collaborative completion of a 2-page communication preferences document between a primary physician and an adolescent/young adult patient. Intervention arm physicians will participate in a 1-hour training led by study PI, [name], featuring didactic, multimedia, and experiential-based learning to support their facilitation of the WE CHATT intervention with patients.

Control Arm. Physicians randomized to the control arm will not receive training in the WE CHATT communication intervention. Usual/standard care will be provided.

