Descriptive Measures. All physician participants will be asked to complete a background/demographic questionnaire (e.g., age, years of practice, previous communication training). Baseline and post-intervention completion of a previously used/published measure of physician comfort in communicating with patients and families, particularly around difficult topics (i.e., prognosis), will also be completed. Medical chart review will be completed to gather patient demographics and basic medical history, which will be used to define the study sample.

Outcome Measures.

Physician Measures. Intervention-arm physician participants will complete an investigator-designed Likert-rating and open-ended question survey assessing intervention satisfaction, ease of intervention administration/completion, time to complete WE CHATT intervention with patient, barriers/feedback specific to WE CHATT, and knowledge gained/perceived impact on practice.

Patient/Caregiver Measures. Intervention-arm patient and caregiver dyads will complete an investigator-designed Likert-rating and open-ended question survey assessing intervention satisfaction, ease of intervention administration/completion, time to complete WE CHATT intervention with physician, barriers/feedback specific to WE CHATT, and knowledge gained/perceived impact on their medical care. All participating patients and parents will complete the self-administered 18-item Service Evaluation Questionnaire⁴⁹ as an assessment of healthcare satisfaction, which has been used in similarly aged samples.⁵⁰ Patient and caregiver versions of previously validated survey tools of trust in physician (PediTIPS) and perceived empathy (CARE measure) will also be completed.

Analysis Plan. Paired samples T-Test will be employed within the intervention arm to compare mean physician comfort, mean patient/family satisfaction, mean trust in physician, and mean perceived empathy. ANCOVA will be used to examine group differences in physician comfort, patient/family satisfaction, trust in physician, and perceived empathy. Frequencies, percentages and means will be calculated to describe physician, patient and family satisfaction with the WE CHATT intervention.

LIMITATIONS

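### Between-arm tests of patient and caregiver scores do not use the randomised physician as the unit, comfort also gets a one-arm pre/post test, and the paired test for the other three outcomes has no defined pair

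*Combined protocol and SAP*

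**What the plan says.** All references are to the combined protocol and SAP.

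- **Allocation** (Recruitment and Sample, Physicians): 20 physicians are recruited, of whom "10 will be randomized to participate in the intervention arm and 10 will be randomized to the control arm".
- **How patients enter** (Patient/Caregivers): a new patient who meets the criteria and is "being cared for by a participating physician will be eligible for the study". One parent or caregiver per patient is also eligible. Neither a number of patients per physician nor a total is given.
- **Timing of comfort** (Descriptive Measures, in a paragraph that opens with all physician participants): "Baseline and post-intervention completion of a previously used/published measure of physician comfort in communicating with patients and families".
- **Timing of satisfaction** (Patient/Caregiver Measures): "All participating patients and parents will complete the self-administered 18-item Service Evaluation Questionnaire". No occasion is given.
- **Timing of trust and empathy** (same place): "Patient and caregiver versions of previously validated survey tools of trust in physician (PediTIPS) and perceived empathy (CARE measure) will also be completed". No occasion is given.
- **Within-arm test** (Analysis Plan): "Paired samples T-Test will be employed within the intervention arm to compare mean physician comfort, mean patient/family satisfaction, mean trust in physician"; the sentence goes on to perceived empathy. What is paired is not said.
- **Between-arm test** (Analysis Plan): "ANCOVA will be used to examine group differences in physician comfort, patient/family satisfaction, trust in physician, and perceived empathy". No covariate, unit of analysis or physician effect is named.
- **Status of these tests** (Study Aims): "The primary outcome of this pilot study is determining feasibility and acceptability".

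**The concern.** Three features of the two planned tests do not fit the design.

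1. **Unit of analysis.** Physicians are randomised, and patients and caregivers are nested under them. Trust and empathy are ratings of the physician, so scores from one physician's patients may well be correlated. An ANCOVA on patient rows with no physician term would then give p-values that are too small and intervals that are too narrow. The label patient/family also leaves room for stacking each patient with the caregiver as two independent observations.
2. **Physician comfort.** A paired test in the intervention arm alone ignores the control physicians. Repeat completion of the scale, growing experience or a division-wide change could all move the mean in both arms. The plan does not say whether a statement about comfort would rest on this test or on the ANCOVA.
3. **The other three outcomes.** Only comfort has two stated occasions. For satisfaction, trust and empathy the pair could be pre/post or patient/caregiver, and two analysts could follow the text and run different tests. The same gap leaves their ANCOVA without a stated baseline covariate.

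At stake is whether the inferential results that a later, larger study might draw on can be carried out as written and mean what they appear to mean.

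**Working it through.** The plan states no alpha, power, effect size or SD, so it has no figure to reproduce. From the documents come 10 v 10 physicians, one caregiver per patient, and two stated occasions for 1 of the 4 outcomes. Assumed for illustration: two-sided 5% tests, ICC 0.05-0.20, 1 to 5 patients per physician (m), within-dyad correlation 0.3-0.7, pre/post correlation r of 0.5-0.7, and a drift shared by both arms.

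**Step 1. Patients treated as independent.** With total SD 1, the true variance of the difference between arm means is (2/10) × (ICC + (1 − ICC)/m). A patient-level test uses 2/(10m). The ratio is the design effect, 1 + (m − 1) × ICC. At m = 5 and ICC 0.20 it is 1 + 4 × 0.20 = 1.80, and the normal approximation 2 × P(Z > 1.96/√1.80) gives 14.4%. Simulation (200,000 runs per cell, no intervention effect):

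| Patients per physician | ICC 0.05 | ICC 0.10 | ICC 0.20 |
|---|---|---|---|
| 1 | 5.0% | 5.0% | 5.0% |
| 2 | 5.5% | 6.2% | 7.4% |
| 3 | 6.2% | 7.3% | 9.9% |
| 5 | 7.3% | 9.8% | 14.6% |
| unequal, 1 to 5 | 6.5% | 8.1% | 11.2% |

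A t-test on one mean per physician (18 df) stays at 4.8-5.1% throughout. At ICC 0.01 the normal approximation for the patient-level test gives only 5.1-5.5% at 2 to 5 patients.

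**Step 2. Patient and caregiver stacked, one dyad per physician.** The design effect is 1 + within-dyad correlation, so 1.3, 1.5 and 1.7 at correlations 0.3, 0.5 and 0.7. The normal approximation gives 8.6%, 11.0% and 13.3%. With the t-test at this sample size the range is about 9-14%.

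**Step 3. Comfort, paired test in one arm, n = 10, no intervention effect.** In units of the comfort SD, the SD of the change is √(2(1 − r)): 1.00 at r = 0.5 and 0.775 at r = 0.7. The noncentrality is drift × √10 / SD of the change.

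| Shared drift (SD) | Noncentrality, r = 0.5 / 0.7 | Significant, r = 0.5 / 0.7 |
|---|---|---|
| 0.2 | 0.632 / 0.816 | 8.8% / 11.3% |
| 0.3 | 0.949 / 1.225 | 13.6% / 19.5% |

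Under the same drift in both arms, the between-arm ANCOVA with baseline comfort as covariate rejects 4.9-5.0% of the time.

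**Step 4. The pair.** Setting the measurement sections against the Analysis Plan: comfort has baseline and post-intervention occasions, so its pair is clear. The Service Evaluation Questionnaire, PediTIPS and CARE have none stated. Comfort's place in the same sentence favours pre/post for all four. The patient and caregiver versions of the trust and empathy tools, and the reference to dyads, make a patient/caregiver pair possible for these three. The text does not decide between them.

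**The case against.** The strongest reply is that this is a pilot whose primary outcome is feasibility and acceptability, and that most of the harm rests on numbers the documents do not give. Much of that stands.

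- **Clustering.** Some of the wording is in the singular, and one patient per physician is not excluded. At one each there is no inflation from physician clustering. The plan also nowhere says that patients will be treated as independent. A reader might infer that the between-arm patient tests are certainly invalid; the documents support only a conditional statement. The gap remains because no number is set, and physician means are valid either way.
- **Comfort.** The between-arm ANCOVA is already planned, baseline data are described, and increased comfort is listed as a future aim. A reader might infer that a comfort claim will rest on the uncontrolled test; nothing says so. What survives is that the plan does not say which result carries the statement.
- **Pairing.** A reader might infer that no second questionnaire was ever intended, or that ratings before first contact are meaningless because patients are new. The documents are silent on a repeat administration and do not define new, so neither inference can be drawn. A dyad comparison is a legitimate possibility, which is why the remedy is to define the pair rather than simply to delete the test.

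The reply does not meet the main point: the sponsor chose to plan inferential tests, and these should match the randomised design.

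**Conclusion.** The concern holds, as something that should be fixed rather than a threat to the pilot's main purpose. Three facts are certain from the text: physicians are randomised and the ANCOVA has no physician term; comfort gets a one-arm pre/post test beside the controlled one; and no pair is defined for 3 of the 4 outcomes.

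The sizes are illustrations under the assumptions listed above. Physician clustering costs nothing at one patient per physician, little at a low ICC, and up to about 15% false positives at 5 patients and ICC 0.20. Pooling dyads would matter even at one patient per physician, but the plan does not say that it will pool. The comfort figures depend on a drift for which the documents give no evidence.

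A reader should not conclude that the feasibility and acceptability results are compromised. The frequencies, percentages and means describing satisfaction with WE CHATT are unaffected.

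**What to change.** Amend the Analysis Plan as follows.

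1. **Patient and caregiver outcomes.** Compare arms on patient scores and on caregiver scores separately, with the physician as the unit: either one mean per physician (18 df if all 20 contribute) or a random physician effect with small-sample degrees of freedom. State the expected number of patients per physician.
2. **Physician comfort.** Rest any statement on the between-arm ANCOVA with baseline comfort as covariate, reported as an adjusted difference with 95% CI. Report within-arm change in both arms as description only.
3. **Satisfaction, trust and empathy.** Define the pair or drop the paired t-test. If it is pre/post, state the occasions, schedule the baseline in both arms and use it as the ANCOVA covariate. If it is patient versus caregiver, label it a dyad comparison and not evidence of an intervention effect.

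**Cost.** Items 1 and 2 change wording only. Item 3 adds a questionnaire administration only if a baseline is wanted and was not already intended; that must be settled before enrolment, because a missed baseline cannot be recovered. Within-arm p-values are given up.

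The intervals are wide. For comfort the half-width is t(0.975, 17) × √(1 − r²) × √(2/10), or 2.110 × 0.866 × 0.447 = 0.82 SD at r = 0.5 and 2.110 × 0.714 × 0.447 = 0.67 SD at r = 0.7. For patient scores without a baseline it is t(0.975, 18) × √(0.2 × (ICC + (1 − ICC)/m)): 0.68-0.73 SD at 2 patients per physician and 0.46-0.56 at 5, against 0.64 and 0.40 if patients were treated as independent. At one patient each it is 0.94 either way. This imprecision belongs to a trial of 20 physicians; the fix makes it visible.

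### Physicians are randomized, but the tests of patient- and caregiver-reported outcomes make no allowance for physician or dyad, so standard errors may be too small

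*Combined protocol and SAP*

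**What the plan says.** All references are to the combined protocol and SAP.

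- **Randomization** (METHODS, Recruitment and Sample, Physicians): of 20 physicians, "10 will be randomized to participate in the intervention arm and 10 will be randomized to the control arm".
- **Patients and caregivers** (Recruitment and Sample, Patient/Caregivers): a new patient who meets the criteria and is "being cared for by a participating physician will be eligible for the study". "One parent/caregiver of patient participants meeting inclusion criteria will also be eligible". No number or cap per physician is given, and no patient total.
- **Intervention** (Procedures, Intervention Arm): the tool is a "communication preferences document between a primary physician and an adolescent/young adult patient".
- **Measures** (Descriptive Measures and Outcome Measures): the only baseline described is "Baseline and post-intervention completion of a previously used/published measure of physician comfort". Patients and parents all complete a satisfaction questionnaire. Trust in the physician and perceived empathy have separate patient and caregiver versions.
- **Analysis** (Analysis Plan): "Paired samples T-Test will be employed within the intervention arm to compare mean physician comfort, mean patient/family satisfaction, mean trust in physician", and likewise perceived empathy. Between arms, "ANCOVA will be used to examine group differences in physician comfort, patient/family satisfaction, trust in physician, and perceived empathy".

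Those two sentences are the whole inferential plan. Covariates are not named, and LIMITATIONS does not mention clustering.

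**The concern.** The same two methods are applied to two kinds of data. Physician comfort gives one value per randomized unit, and there ANCOVA and the paired t-test are in order. Satisfaction, trust and empathy come from people who sit under the randomized unit. Trust and empathy are ratings of the physician, so two patients of one physician may well score alike. A patient and that patient's caregiver may also score alike.

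Both tests assume independent observations. Run on individual respondents, they understate the standard error in either of two cases:

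- **(a)** several physicians contribute more than one patient, and ratings (for the paired test, changes) under the same physician are positively correlated;
- **(b)** correlated patient and caregiver scores are pooled into one analysis.

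P-values and confidence intervals would then look more certain than 20 physicians between arms, or 10 within the intervention arm, can support.

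**Working it through.** **Inputs.** From the documents: 10 physicians per arm and one caregiver per patient. Not in the documents, so assumed: two-sided 5% level; *m* = 1, 2, 3 or 5 patients per physician; ICC among patients of one physician 0.05 to 0.20; patient–caregiver correlation *r* 0.3 to 0.5. The plan states no alpha, power or patient number, so it has no figure of its own to reproduce.

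**Formulas.**
- Patients and caregivers analysed separately: design effect DE = 1 + (*m* − 1) × ICC.
- Pooled dyads: DE = 1 + *r* + 2(*m* − 1) × ICC.
- True SE ÷ naive SE ≈ √DE.
- Large-sample type I error = 2 × [1 − Φ(1.96/√DE)].

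Example, *m* = 5 and ICC = 0.20: DE = 1 + 4 × 0.20 = 1.80; √1.80 = 1.342; 1.96/1.342 = 1.461; type I error = 14.4%.

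**Separate analyses, equal numbers per physician, no covariate.** Ranges run over ICC 0.05 to 0.20. The last two columns come from null simulations. For the paired test the ICC is that of the change scores.

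| *m* | DE | Formula | Simulated, between arms | Simulated, paired |
|---|---|---|---|---|
| 1 | 1.00 | 5.0% | 4.9% | 5% |
| 2 | 1.05–1.20 | 5.6–7.4% | 5.6–7.5% | 5.5–7.1% |
| 3 | 1.10–1.40 | 6.2–9.8% | 6.3–9.7% | 6.4–9.9% |
| 5 | 1.20–1.80 | 7.4–14.4% | 7.6–14.5% | 7.3–14.5% |

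The ICC of changes could be lower than that of the scores, because stable physician effects cancel.

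**Uneven numbers, between arms, simulated.** One of 20 physicians with two patients and the rest with one: 4.9–5.3%, negligible. Ten of 20 with two: 5.6–6.4%. Ten of 20 with three: 5.8–8.7%. One to five each: 6.5–11.5%.

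**Only if dyads are pooled** (formula; simulations agree within about one percentage point):

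| Dyads per physician | DE | Type I error |
|---|---|---|
| 1 | 1.30–1.50 | 9–11% |
| 3 | 1.50–2.30 | 11–20% |
| 5 | 1.70–3.10 | 13–27% |

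**Covariate check.** The plan names none, so this is a sensitivity check only. With *m* = 5, ICC 0.20 and a covariate correlated 0.5 with the outcome, the between-arm error was 17.0% if the covariate is unrelated to physician and 14.5% if it shares the outcome's ICC.

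**After the fix.** Tests on physician-level means gave 4.7–5.2% in every no-covariate scenario.

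**The case against.** The strongest reply is that this is an unstated detail and not a demonstrated error. The tool is described with one physician and one patient, so one patient per physician is a fair reading. Trust and empathy have separate patient and caregiver versions, and the only hint of pooling is the combined label for patient and family satisfaction. With one patient per physician and separate analyses, DE = 1 and the plain methods are valid. That stands. It makes the point conditional and makes the pooled figures the least certain. But enrolment is open, the text elsewhere speaks of patients in the plural, and nothing commits the plan to one patient each or to separate analyses.

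A second reply concerns the paired test: no baseline is described for patients or caregivers, so what is paired is undefined. That also stands, and the within-arm figures apply only if change scores exist. If the pairing were patient with caregiver, the dyad would be handled but the physician would not.

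A third is that this is a pilot with feasibility and acceptability as its primary outcome, and no decision rule rests on these tests. That is right and limits the consequence. The tests are still planned, and their p-values and intervals may be read as early signals for a later trial.

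**Conclusion.** The concern holds in its conditional form. The plan randomizes physicians, leaves patients per physician open, and specifies methods without a physician or dyad term for outcomes nested under the physician. With one patient per physician and separate analyses there is no problem. With two to five patients each, the nominal 5% between-arm error becomes roughly 6% to 14.5%; pooling dyads takes it from about 9% up to 27%. These sizes rest wholly on the assumed ICC, cluster size and dyad correlation; the documents neither support nor exclude them.

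Only the inferential comparisons of satisfaction, trust and empathy are affected. The primary outcome, the descriptive satisfaction results and both physician-comfort tests are not. It should be fixed, but it does not threaten the pilot's main purpose.

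**What to change.** In the Analysis Plan:

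1. State the planned number of patients per physician, the unit of analysis, the ANCOVA covariates, and what is paired for patient and caregiver outcomes.
2. Analyse patient and caregiver scores separately. If they are pooled, add a dyad random effect; with one dyad per physician this is the same term as the physician effect.
3. Between arms, wherever physicians contribute more than one patient, compare physician-level means or fit a linear mixed model with a physician random intercept and Kenward–Roger or Satterthwaite degrees of freedom.
4. Within the intervention arm, test physician-level mean changes (9 df if all 10 physicians contribute) or fit the same mixed model to the changes.
5. Keep ANCOVA and the paired t-test for physician comfort. Keep them also for separate patient and caregiver analyses if the plan is one patient per physician, and in that case say so.
6. Where physicians have several patients, report the ICC with its interval. It will be wide: for an estimate of 0.10 with three patients each, F = 1.2/0.9 = 1.333 on 18 and 40 df gives about −0.14 to 0.42.

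Reporting these comparisons descriptively, without tests, would be a simpler alternative.

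**Cost.** Wording only; no extra data or participants. Intervals widen. With separate analyses, between-arm intervals from physician means are about 6% wider at *m* = 2, ICC 0.05 (1.025 × 2.101/2.024 = 1.06) and 42% wider at *m* = 5, ICC 0.20 (1.342 × 2.101/1.984 = 1.42). Simulated paired intervals are about 9% to 49% wider over the same range. The mixed model can be slightly conservative at low ICC (type I error 4.2–5.0% between arms, 3.8–5.0% paired).

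### The Analysis Plan tests four effect constructs that the Study Aims defer to the future, with no exploratory label and no interval estimates

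*Combined protocol and SAP*

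**What the plan says.** All references are to the combined protocol and SAP.

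- **Study Aims.** "The primary outcome of this pilot study is determining feasibility and acceptability, however, in the future, WE CHATT aims to" improve communication with young patients and raise physician comfort. Effect is thus a later goal, not one for this pilot.
- **Recruitment and Sample, Physicians.** "10 will be randomized to participate in the intervention arm and 10 will be randomized to the control arm". The total of 20 is supported only by the expressed willingness of faculty and fellows to take part. No alpha, power, effect size or precision target is given. The number of patients per physician is not stated.
- **Descriptive Measures.** "Baseline and post-intervention completion of a previously used/published measure of physician comfort in communicating with patients and families" is planned for all physicians. No baseline is stated for satisfaction, trust or empathy.
- **Outcome Measures, Patient/Caregiver Measures.** Three constructs have two respondents each. For satisfaction, "All participating patients and parents will complete the self-administered 18-item Service Evaluation Questionnaire". For the other two, "Patient and caregiver versions of previously validated survey tools of trust in physician (PediTIPS) and perceived empathy (CARE measure) will also be completed".
- **Analysis Plan.** Within the intervention arm: "Paired samples T-Test will be employed within the intervention arm to compare mean physician comfort, mean patient/family satisfaction, mean trust in physician", and also perceived empathy. Between arms: "ANCOVA will be used to examine group differences in physician comfort, patient/family satisfaction, trust in physician, and perceived empathy". Satisfaction with the intervention itself is summarised descriptively.

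The Analysis Plan does not call the effect comparisons exploratory, plans no confidence intervals, and does not say whether patient and caregiver scores are combined.

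**The concern.** The inferential part of the analysis is spent on questions that the aims set aside, while the declared primary outcome is handled descriptively. Estimating effects in a pilot is reasonable. The weakness is that the plan names only significance tests and says nothing about how their results may be used.

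With so few randomised physicians, a non-significant difference in comfort could be taken to mean that the tool does not work, and a single significant one that it does. The data could support neither statement. A p-value alone also gives the designers of the next trial little to work with. They need differences, standard deviations and an honest width of uncertainty.

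**Working it through.** The documents give no statistical basis for 20 physicians, so there is no planned figure to reproduce.

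**Inputs from the documents:** 10 physicians per arm; four constructs (comfort, satisfaction, trust, empathy); two respondents for the last three; a stated baseline for comfort only.

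**Assumptions, because the documents are silent:** two-sided alpha 0.05 per test; true difference 0.5 SD (0.8 SD also shown); correlation r between baseline and outcome of 0.5 (0.7 also shown); no dropout; intraclass correlation (ICC) 0.05 to 0.20 and 1 to 10 patients per physician.

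**1. How many tests can be run.** A paired t-test needs two measurements. Only comfort has a stated pair, so one paired test is defined. The between-arm comparisons need only a post-intervention score, although no covariate is named for satisfaction, trust or empathy.
- Respondents pooled: 1 paired + 4 between-arm = 5.
- Respondents separate: 1 paired + (1 + 3 + 3) between-arm = 8.

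**2. Chance of at least one significant result when nothing works.** Under independence this is 1 − 0.95^k.
- k = 5: 1 − 0.774 = 22.6%.
- k = 8: 1 − 0.663 = 33.7%.

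The tests share data, so independence is an upper case. Simulation with eight equally correlated tests gives 25% at correlation 0.5 and 19% at 0.7.

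**3. Precision and power for physician comfort, 10 v 10.** The standard error in SD units is √(2/10) = 0.447 unadjusted, and 0.447 × √(1 − r²) with ANCOVA. The half-width is t × SE, with 18 df unadjusted and 17 df with ANCOVA. Power is from the noncentral t.

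| Analysis | 95% CI half-width (SD) | Power at 0.5 SD | Power at 0.8 SD | Difference with 80% power (SD) |
|---|---|---|---|---|
| Unadjusted | 2.101 × 0.447 = 0.94 | 18.5% | 39.5% | 1.32 |
| ANCOVA, r = 0.5 | 2.110 × 0.447 × 0.866 = 0.82 | 23.0% | 49.5% | 1.15 |
| ANCOVA, r = 0.7 | 2.110 × 0.447 × 0.714 = 0.67 | 31.5% | 65.6% | 0.95 |

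The half-width is also the smallest observed difference that reaches significance. If the true difference is 0.5 SD, a significant estimate must be at least 0.94/0.5 = 1.9 times too large unadjusted, 0.82/0.5 = 1.6 times at r = 0.5, and 0.67/0.5 = 1.3 times at r = 0.7.

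**4. Patient and caregiver scores.** Here 10 per arm is the number of clusters. With m patients per physician the design effect is 1 + (m − 1) × ICC, and the effective number per arm is 10m divided by it. Power at 0.5 SD, with 18 df:
- m = 1: 18.5%.
- m = 5, ICC 0.20: 50/1.8 = 27.8 effective per arm, 42%.
- m = 5, ICC 0.05: 50/1.2 = 41.7 effective per arm, 58%.
- m = 10, ICC 0.05: 100/1.45 = 69.0 effective per arm, 79%.

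If clustering is ignored, the true alpha of a nominal 0.05 test runs from 0.056 (m = 2, ICC 0.05) to 0.144 (m = 5, ICC 0.20).

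**The case against.** Pilots commonly report secondary comparisons. The Study Aims already rank feasibility and acceptability above them, and the Analysis Plan speaks only of examining differences. It claims no efficacy and sets no progression rule. That stands: nothing shows an intention to misuse a p-value, and the effect measures are unranked only among themselves. It does not supply the missing label or intervals.

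Four stronger readings are tempting, and the documents do not support them.

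- **That the plan runs 8 to 14 tests, with a false-positive chance of up to 51%.** Two methods on four constructs gives 8 by name, and two methods on seven respondent-level outcomes gives 14 (1 − 0.95^14 = 51.2%). But the paired tests on satisfaction, trust and empathy have no stated pair, so the upper count includes tests for which the plan describes no data.
- **That an isolated significant result is probably chance.** The figures in step 2 are not the probability that a given finding is false. That depends on how often such effects are real. With 23% power, the false share of significant results is 0.025/(0.025 + 0.115) = 18% if half of the tested effects are real at 0.5 SD, and 0.045/(0.045 + 0.023) = 66% if a tenth are. Exaggeration of a moderate true effect is the firmer point.
- **That null results are uninformative for every outcome.** This is shown for physician comfort only. For the other three constructs it turns on numbers that the plan omits.
- **That pooling would dilute the youth response, or that patient scores should come first.** The plan does not say that scores are pooled, no dilution can be computed, and the aims list physician comfort beside communication.

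A ban on p-values would also be a reporting preference. The label and the intervals do the necessary work.

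**Conclusion.** The point holds in a limited form. The analysis tests effects that the aims defer, without an exploratory label or interval estimates. As written, about 5 to 8 tests are runnable, with a 23% to 34% chance of at least one significant result under no effect if independent, and less if correlated.

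For physician comfort the consequence is firm across the assumed range. Even at r = 0.7 the interval extends 0.67 SD either side and power at 0.5 SD is 31.5%. Neither a null nor an isolated significant result can then be read as evidence about effect. For patient and caregiver outcomes the conclusion is conditional on patients per physician and on ICC. Alpha, effect size, r, ICC and cluster size are all assumptions.

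This does not threaten the feasibility and acceptability outcome. It limits what the effect analyses can say, and it is cheap to put right.

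**What to change.** Replace the paired t-test and ANCOVA sentences in the Analysis Plan with:

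> Between-arm differences will be estimated with 95% confidence intervals, with arm means and SDs, separately for physicians, patients and caregivers; baseline-adjusted for physician comfort, and allowing for clustering by physician for patient and caregiver scores. These analyses are exploratory and will not support efficacy claims or decide progression.

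The descriptive summary of satisfaction with the intervention stays as it is. ANCOVA remains a suitable way to obtain the adjusted comfort difference. The clustering clause is needed because intervals that ignore it would be too narrow for patient and caregiver scores.

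The cost is a change of wording: no extra participants, data or procedures. The downside is that the pilot can claim no significant effect.
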